**Infections or predisposition to infections**

25. Has a history of chronic or recurrent infectious disease, including but not limited to chronic renal infection, chronic chest infection (eg, bronchiectasis), recurrent urinary tract infection (recurrent pyelonephritis or chronic nonremitting cystitis), fungal infection (mucocutaneous candidiasis), or open, draining, or infected skin wounds or ulcers.
26. Has or has had a serious infection (eg, sepsis, pneumonia or pyelonephritis), or has been hospitalized or received IV antibiotics for an infection during the 2 months before screening.
27. Has or has had herpes zoster within the 2 months before screening.
28. Have a history of latent or active granulomatous infection, including TB, histoplasmosis, or coccidioidomycosis, prior to screening.
29. Has had a nontuberculous mycobacterial infection.
30. Has ever had an opportunistic infection (eg, cytomegalovirus colitis or retinitis, pneumocystosis pneumonia, or invasive aspergillosis).
31. Has persistently indeterminate (indeterminate on repeat sampling) QuantiFERON-TB test results. Indeterminate results should be handled as described in Section 8, Study Assessments and Procedures.
32. Is infected with human immunodeficiency virus (HIV, positive serology for HIV antibody).
33. Tests positive for antibodies to hepatitis C virus (HCV) at screening.
34. Tests positive for hepatitis B virus (HBV) infection ([Appendix 6](#) [Section 10.6]).
35. Has a documented history of immune deficiency syndrome (eg, severe combined immunodeficiency syndrome, T cell deficiency syndromes, B cell deficiency syndromes and chronic granulomatous disease).

**Note: For COVID-19-related exclusion, see Exclusion Criterion 42.**

**Malignancy or increased potential for malignancy**

36. Has a known history of lymphoproliferative disease, including lymphoma; a history of monoclonal gammopathy of undetermined significance (MGUS); or signs and symptoms suggestive of possible lymphoproliferative disease, such as lymphadenopathy or splenomegaly.
37. Has any known malignancy or a history of malignancy.

**Other exclusion criteria**

38. Is unable or unwilling to undergo multiple venipunctures because of poor tolerability or lack of easy access to veins.
39. Lives in an institution on court or authority order.
40. Has any condition that, in the opinion of the investigator, would make participation not be in the best interest (eg, compromise the well-being) of the participant or that could prevent, limit, or confound the protocol-specified assessments.
41. Is an employee of the investigator or study site, with direct involvement in the proposed study or other studies under the direction of that investigator or study site, as well as family members of the employees or the investigator.

42. COVID-19 infection:

During the 6 weeks prior to baseline, has had **any** of the following (regardless of vaccination status): (a) confirmed severe acute respiratory syndrome coronavirus 2 (SARS-CoV-2) infection (test positive) **OR** (b) suspected SARS-CoV-2 infection (clinical features of COVID-19 without documented test results) **OR** (c) close contact with a person with known or suspected SARS-CoV-2 infection

- Exception: may be included with a documented negative result for a validated SARS-CoV-2 test

i) obtained at least 2 weeks after conditions (a), (b), (c) above (timed from resolution of key clinical features if present, [eg, fever, cough, dyspnea])

AND

ii) with absence of all conditions (a), (b), (c) above during the period between the negative test result and the baseline study visit

Note on COVID-related exclusion:

- The field of COVID-related testing (for presence of, and immunity to, the SARS-CoV-2 virus) is rapidly evolving. Additional testing may be performed as part of screening and/or during the study if deemed necessary by the investigator

and in accordance with current regulations/guidance from authorities/standards of care.

Precaution: for those who may carry a higher risk for severe COVID-19 illness, follow guidance from local health authorities when weighing the potential benefits and risks of enrolling in the study, and during participation in the study.

**NOTE:** Investigators should ensure that all study enrollment criteria have been met at screening. If a participant's clinical status changes (including any available laboratory results or receipt of additional medical records) after screening but before the first dose of study intervention is given such that he or she no longer meets all eligibility criteria, then the participant should be excluded from participation in the study. Section 5.4, Screen Failures, describes options for retesting. The required source documentation to support meeting the enrollment criteria are noted in [Appendix 2](#) (Section 10.2), Regulatory, Ethical, and Study Oversight Considerations.

### 5.3. Lifestyle Considerations

Potential participants must be willing and able to adhere to the following lifestyle restrictions during the course of the study to be eligible for participation:

1. a girl of childbearing potential who is heterosexually active must remain on a highly effective method of birth control (Inclusion Criterion 5) during the study and for at least 12 weeks after receiving the last administration of study intervention.
2. all girls must agree not to donate eggs (ova, oocytes) during the study and for a period of at least 12 weeks following the last administration of study intervention.
3. a boy who is sexually active with a female of childbearing potential and has not had a vasectomy must agree to use a barrier method of birth control (ie, male condom, female diaphragm or cervical cap, or condom, Inclusion Criterion 8) during the study and for at least 12 weeks after receiving the last administration of study intervention.
4. all boys must agree to not donate sperm during the study and for at least 12 weeks after receiving the last administration of study intervention.
5. participants must not receive a live virus or bacterial vaccination (except for varicella and MMR vaccines prior to first administration of study intervention), during the study and for 3 months after the last administration of any study intervention. See Lifestyle Consideration 6 for information regarding BCG vaccination.
6. participants must not receive a BCG vaccination during the study and for 12 months after the last administration of any study intervention.
7. participants must comply with restrictions on concomitant medications and therapies specified in the protocol (refer to Section 6.5, Concomitant Therapy for details).

8. participants must avoid prolonged sun exposure and avoid use of tanning booths or other UV light sources during the study.
9. participants are recommended to be up to date on all age-appropriate vaccinations prior to screening per routine local medical guidelines. It is strongly recommended that participants will have completed a locally-approved (including emergency use-authorized) COVID-19 vaccination regimen at least 2 weeks prior to study-related visits or procedures. Study participants should follow applicable local vaccine labelling, guidelines, and standards-of-care for participants receiving immune-targeted therapy when determining an appropriate interval between vaccination and study enrollment (see also Section 5.2).

#### **5.4. Screen Failures**

##### **Participant Identification, Enrollment, and Screening Logs**

The investigator agrees to complete a participant identification and enrollment log to permit easy identification of each participant during and after the study. This document will be reviewed by the sponsor study-site contact for completeness.

The participant identification and enrollment log will be treated as confidential and will be filed by the investigator in the study file. To ensure participant confidentiality, no copy will be made. All reports and communications relating to the study will identify participants by participant identification and date of birth (as allowed by local regulations). In cases where the participant is not randomized into the study, the date seen and date of birth (as allowed by local regulations) will be used.

The investigator must also complete a participant screening log, which reports on all participants who were seen to determine eligibility for inclusion in the study.

If, during the screening phase, a participant has not met all inclusion criteria or has met any exclusion criteria or is unable or unwilling to adhere to the prohibitions and restrictions of the study, the participant is considered to be a screen failure and is not eligible to be randomized or enrolled in the study.

In general, if a participant is a screen failure, but at some point in the future meets all of the participant eligibility criteria, the participant may be rescreened after a new informed consent has been obtained. Participants who are rescreened will be assigned a new participant number and will restart a new screening phase. Rescreening will be permitted once.

## 6. STUDY INTERVENTION

### 6.1. Study Interventions Administered

Designation	Product	
Investigational Medicinal Product(s)	Guselkumab Authorization status in the EU/EEA:	
	Authorized	
	Unauthorized	X
	Placebo Authorization status in the EU/EEA:	
	Authorized	
	Unauthorized	X
	Etanercept Authorization status in the EU/EEA:	
	Authorized	X
	Unauthorized	

Guselkumab or placebo will be administered SC using a sponsor-supplied, single use administration device. This will be either the CCI PFS assembled with the UltraSafe Plus™ Passive Needle Guard (PFS-U) device, designed to deliver a single, fixed dose of CCI, or a CCI. Identical devices containing placebo will be used to deliver a volume equivalent to that of active treatment for participants randomized to the placebo arm. Guselkumab will be supplied as a CCI solution of guselkumab in a single-use CCI or CCI PFS. The PFS-U is assembled with a PFS containing 1.0 mL of study intervention and the CCI.

Participants will receive a dose based on body weight. At each dosing visit, participant weight will be measured and the dose of guselkumab will be adjusted accordingly. Participants will receive 1 of the following dose levels depending on their weight:

- Weight <70 kg: CCI administered CCI
- Weight ≥70 kg: CCI administered using the PFS-U

Placebo for guselkumab will also be supplied in a PFS assembled with either the UltraSafe Plus™ Passive Needle Guard or the CCI. Participants who weigh <70 kg will receive 1 or 2 injections of either guselkumab or placebo with a volume(s) determined using the weight-based dose calculation for guselkumab. In Part 2 of the study, participants or their caregiver will be given the option to self-administer guselkumab at the study site. Participants must be ≥12 years of age to self-administer guselkumab.

Commercially available etanercept (25 mg powder and solvent for solution for injection and 50 mg prefilled syringes) will be supplied and administered subcutaneously based on body weight:

- <63 kg: 0.8 mg/kg once weekly using powder and solvent for solution for injection.
- ≥63 kg: 50 mg once weekly administered using a prefilled syringe.

Participants receiving etanercept or their caregiver will also be given the option to self-administer study injections either at the study site when a visit is scheduled or at-home for doses required between regular visits. Participants who weigh <63 kg will receive 1 or 2 injections with a volume(s) determined using the weight-based calculation for etanercept.

Study staff will receive training on study intervention administration using either PFS-U or CCI, which must be documented. For participants/caregivers who will self-administer, training on study intervention administration will be provided by study staff. This will include education regarding instructions for use (IFU), proper handling and storage of devices, guidance on study intervention injection, and proper handling and accounting for used devices. Required storage conditions and expiration date are indicated on the label.

At any time, if participants or caregivers are uncertain about how to administer the study intervention or have questions regarding self-administration, the sponsor recommends that study staff review the IFU with the participant/caregiver along with practice injections with a training device if necessary. Patients or caregivers may be retrained at any time during the study, including if there is a use issue reported by the patient or caregiver. If at any time there is a change in the device required for dosing (eg, CCI to PFS-U) due to a change in a participant's body weight, and the participant/caregiver wishes to continue with self-administration, they must receive training on the new device and the participant/caregiver using the device must be witnessed self-administering a successful injection by study staff prior to performing self-administration.

Different sites should be used for consecutive injections or for two injections administered on the same day. Sites that are tender for any reason should be avoided. Study intervention and injections of other concomitant medications should be given at different anatomic sites.

Details on dose preparation and administration can be found in the Study Site Investigational Product Procedures Manual.

## Part 1

### *Week 0 to Week 16 (Placebo-Controlled Period)*

The guselkumab and placebo administrations will be administered by site personnel at the study site. Etanercept will be administered at the study site at Week 0. Subsequent weekly doses of etanercept through Week 15 may be administered at the study site or be self-administered at home by the participant or caregiver on weeks without a site visit. The dose regimens are as follows:

- **Group I:** Weight-based guselkumab dose up to CCI SC at Weeks 0, 4, and 12.
- **Group II:** Weight-based placebo for guselkumab dose administered SC at Weeks 0, 4, and 12.
- **Group III:** Weight-based etanercept dose up to 50 mg SC weekly through Week 15.

***Week 16 through Week 52 (Withdrawal and Retreatment Period)***

- **Group Ia:** Participants randomized to guselkumab who are PASI 90 responders at Week 16 will not receive any additional doses of guselkumab until they lose  $\geq 50\%$  of their Week 16 PASI improvement, at which time they will receive a weight-based guselkumab SC dose, followed by a dose 4 weeks later, and q8w thereafter through Week 52.
- **Group Ib:** Participants randomized to guselkumab who are PASI 90 nonresponders at Week 16 will receive a placebo SC injection at Week 16 and continue treatment with guselkumab SC q8w from Week 20 through Week 52.
- **Group IIa:** Participants randomized to placebo who are PASI 90 responders at Week 16 will not receive any additional doses of study intervention until they lose  $\geq 50\%$  of their Week 16 PASI improvement, at which time they will receive a weight-based guselkumab SC dose, followed by a dose 4 weeks later, and q8w thereafter through Week 52.
- **Group IIb:** Participants randomized to placebo who are PASI 90 nonresponders at Week 16 will receive a weight-based guselkumab SC dose at Weeks 16 and 20, followed by q8w dosing thereafter through Week 52.
- **Group III:** Participants randomized to etanercept who elect to continue in the study will receive a weight-based guselkumab SC dose at Weeks 20 and 24, followed by q8w dosing thereafter through Week 48.

Participants in any of the treatment groups who elect to end study participation at Week 52 and not participate in the LTE will not receive any administration of study intervention at Week 52 and should return to the site 12 weeks after receiving the last administration of study intervention for a safety follow-up visit.

**Part 2**

Participants enrolled in Part 2 of the study will receive a weight-based dose of open-label guselkumab SC at Weeks 0, 4 and q8w thereafter through Week 52. Participants in Part 2 of the study who elect to end study participation at Week 52 and not participate in the LTE will not receive any administration of study intervention at Week 52 and should return to the site 12 weeks after receiving the last administration of study intervention for a safety follow-up visit.

In Part 2 of the main study, participants or their caregiver will be given the option to self-administer study injections at the study site using the appropriate presentation (either PFS-U or CCI). Participants must be at least 12 years of age to self-administer study injections. Participants or their caregivers will be trained on proper use of the device(s) and deemed capable, as determined by study staff. Otherwise injections will continue to be performed by study staff.

**Long-term Extension (From Week 52 until study termination)**

Following completion of the Week 52 visit, participants who have had a beneficial response from guselkumab treatment as determined by the investigator, and are willing to continue guselkumab treatment, may enter the LTE of the study. Participants who decide to participate in the LTE will continue to receive guselkumab at Week 52 and q8w thereafter until one of the following occurs:

- The participant turns 18 years of age and resides in a country where marketing authorization has been granted for guselkumab treatment of plaque psoriasis in adult patients, and have had the opportunity to complete up to 1 year in the LTE.
- Marketing authorization is obtained for guselkumab for treatment of plaque psoriasis for patients  $\geq 6$  to  $< 18$  years of age in the participant's country of residence.
- Marketing authorization is denied for guselkumab for the treatment of plaque psoriasis for patients  $\geq 6$  to  $< 18$  years of age in the participant's country of residence.
- A company decision is made to no longer pursue an indication in plaque psoriasis in the pediatric population ( $\geq 6$  to  $< 18$  years of age) in the participant's country of residence.

Participants in Part 1 who continue in the LTE portion of the study will receive guselkumab as follows:

- Participants withdrawn from guselkumab or placebo at Week 16 who meet loss of response criteria and are retreated with or initiated guselkumab prior to Week 52 and receive guselkumab at Week 48 will not receive study intervention administration at Week 52 and will resume guselkumab administration at Week 60 and q8w thereafter.
- Participants who meet loss of response criteria at Week 48 will receive guselkumab at Weeks 48 and 52 followed by q8w administration beginning at Week 60.
- Participants withdrawn from treatment at Week 16 who have not been retreated with guselkumab prior to Week 52 will receive a weight-based guselkumab dose at Week 52 and q8w thereafter.

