- i. Participants randomized to etanercept will receive an etanercept dose weekly from Week 0 through Week 15. Participants will have the option of returning to the study site weekly for dose administration or the option to self-administer at home for the weeks when no regular site visit is scheduled (ie, Weeks 1, 2, 3, 5, 6, 7, 9, 10, 11, 13, 14, and 15). Participants who decide to administer etanercept at home will record study drug administration information on a paper questionnaire. Participants randomized to etanercept will then have the option to initiate a weight-based guselkumab dose regimen with injections at Week 20 and 24 followed by q8w administration through Week 48 or terminate study participation after a study termination visit at Week 28.
- j. PASI 90 responders withdrawn from treatment at Week 16 who have not met loss of response criteria prior to Week 52 and are continuing into the long-term extension of the study will receive guselkumab at Week 52 followed by q8w administration beginning at Week 60 in the long-term extension. Participants withdrawn from treatment at Week 16 who met loss of response criteria prior to Week 48 and received a guselkumab dose at Week 48 and continue into the long-term extension will receive their next administration of guselkumab at Week 60 followed by q8w thereafter. Participants who meet loss of response criteria at Week 48 will receive a weight-based dose of guselkumab at Week 48 followed by a dose at Week 52 and q8w administration starting at Week 60.
- k. Vital signs include heart rate, blood pressure, and temperature.
- l. Girls of childbearing potential must have a negative urine pregnancy test before randomization and at all study visits through Week 16. After Week 16 a negative urine pregnancy test is required at all visits at which study intervention is to be administered.
- m. Head circumference will be measured for participants  $\geq 6$  to  $< 12$  years of age
- n. Pain experienced with each placebo or guselkumab injection will be assessed at each study visit at which an injection is administered. Pain will be assessed using the Faces Pain Scale-Revised for injection pain in children  $\geq 6$  to  $< 12$  years of age (Appendix 17 [Section 10.17]), and the linear Injection Pain Visual Analog Scale for adolescents  $\geq 12$  to  $< 18$  years of age (Appendix 18 [Section 10.18]).

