### 1.3.3. Long-term Extension Phase (Week 60 Through Study Completion/Termination)

Phase	Long-term Extension				Study Completion/Termination Visit c
	Week 60	q8w visit	q24w visit a	q48w visit b	
Study Proceduresd					
Study Intervention Administration					
Administration e	X	X	X	X	
Safety Assessments					
Physical examination (including skin exam)				X	X
Vital signs f	X	X	X	X	X
Tuberculosis evaluation	X	X	X	X	X
Urine pregnancy test g	X	X	X	X	X
Height				X	X
Weight	X	X	X	X	X
C-SSRS h	X	X	X	X	X
Concomitant therapy	X	X	X	X	X
Adverse events	X	X	X	X	X
Efficacy Assessments					
IGA i	X		X	X	X
PASI i	X		X	X	X
Body surface area (BSA)% i	X		X	X	X
Clinical Laboratory Assessment					
Hematology j	X		X	X	X
Chemistry j,k	X		X	X	X
Pharmacokinetics and Immunogenicity					
Serum guselkumab concentration					X
Antibodies to guselkumab					X

BSA=body surface area; C-SSRS=Columbia-Suicide Severity Rating Scale; IGA=Investigator's Global Assessment; LTE=long-term extension; PASI=Psoriasis Area and Severity Index.

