### **Long-Term Extension Phase**

Following completion of the Week 52 visit, participants who have had a beneficial response from guselkumab treatment as determined by the investigator, and are willing to continue guselkumab treatment, may enter the LTE of the study. Participants who decide to participate in the LTE will continue to receive guselkumab q8w until one of the following occurs:

- The participant turns 18 years of age and resides in a country where marketing authorization has been granted for guselkumab treatment of plaque psoriasis in adult patients, and have had the opportunity to complete up to 1 year in the LTE.
- Marketing authorization is obtained for guselkumab for treatment of plaque psoriasis for patients  $\geq 6$  to  $< 18$  years of age in the participant's country of residence.
- Marketing authorization is denied for guselkumab for the treatment of plaque psoriasis for patients  $\geq 6$  to  $< 18$  years of age in the participant's country of residence.
- A company decision is made to no longer pursue an indication in plaque psoriasis in the pediatric population ( $\geq 6$  to  $< 18$  years of age) in the participant's country of residence.

All participants will begin q8w administration of guselkumab at Week 52, except for participants who have initiated or been retreated with guselkumab prior to Week 48 and receive a guselkumab injection at Week 48. Those participants will receive their first dose of guselkumab in the LTE at Week 60 and q8w thereafter. Participants who are retreated with or initiate guselkumab treatment at Week 48 will also receive a guselkumab dose at Week 52 followed by q8w administration beginning at Week 60. The same guidance for self-administration in Part 2 applies to the LTE.

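### Protocol Sections 6.1 and 8 give etanercept crossovers different next doses on entering the extension: Week 52 or Week 60

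*Protocol*

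**What the plan says.** Main-study dosing for etanercept crossovers (Group III) is clear. Section 6.1 gives them "a weight-based guselkumab SC dose at Weeks 20 and 24, followed by q8w dosing thereafter through Week 48". Footnote i to the Part 1 Schedule of Activities (Section 1.3.1) agrees: "followed by q8w administration through Week 48 or terminate study participation".

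Two places then say what happens on entry to the extension.

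- **Section 6.1, Long-term Extension.** Participants who join "will continue to receive guselkumab at Week 52 and q8w thereafter". Three bullets follow for Part 1. The first removes the Week 52 dose and resumes at Week 60, but only for those "withdrawn from guselkumab or placebo at Week 16 who meet loss of response criteria and are retreated with or initiated guselkumab prior to Week 52" who also have a Week 48 dose. The second covers loss of response at Week 48 (doses at Weeks 48, 52 and 60). The third covers those withdrawn at Week 16 and not retreated before Week 52. No bullet mentions etanercept.
- **Section 8, Long-Term Extension Phase.** Week 52 is the starting point for everyone "except for participants who have initiated or been retreated with guselkumab prior to Week 48 and receive a guselkumab injection at Week 48". For that group: "Those participants will receive their first dose of guselkumab in the LTE at Week 60 and q8w thereafter".

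Footnote j to Section 1.3.1 also has a Week 60 rule, but limits it to "Participants withdrawn from treatment at Week 16 who met loss of response criteria prior to Week 48 and received a guselkumab dose at Week 48". The extension schedule in Section 1.3.3 is titled "Long-term Extension Phase (Week 60 Through Study Completion/Termination" and does not say who skips Week 52.

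**The concern.** The same children fall under two dosing rules in one protocol, and a site cannot follow both. Under Section 6.1 a crossover gets an additional biologic injection 4 weeks after the previous one, although maintenance is every 8 weeks. Under Section 8 the gap is 12 weeks. Compliance with either section departs from the other, so classifying an incorrect dose as a major deviation (SAP Section 4.5) becomes arbitrary.

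Two analyses depend on which rule was followed:

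- The extension efficacy summary (SAP Section 5.5.2.3) pools everyone who entered the extension. IGA, PASI and BSA at Week 60 are taken before dosing, so a crossover's Week 60 value is read at a different time since the last dose under each rule.
- The extension safety set (SAP Section 2.4.2) requires an injection at or after Week 52. A crossover who leaves between Weeks 52 and 60 is in the set under Section 6.1 and out of it under Section 8.

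**Working it through.** The documents state no figure to reproduce. The check is a dosing calendar.

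**Crossover doses in the main study.** Weeks 20 and 24, then every 8 weeks: 24 + 8 = 32, 32 + 8 = 40, 40 + 8 = 48. The first guselkumab dose is at Week 20 and the last at Week 48.

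**Applying each section:**

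| | Section 6.1 as written | Section 8 |
|---|---|---|
| Does the exception apply? | No: limited to those withdrawn from guselkumab or placebo at Week 16 | Yes: started at Week 20, dosed at Week 48 |
| Doses from Week 48 | 48, 52, 60, 68 | 48, 60, 68 |
| Gap after Week 48 | 52 − 48 = 4 weeks | 60 − 48 = 12 weeks |
| Doses in Weeks 48 to 60 | 3 | 2 |
| Time since last dose at the Week 60 reading | 60 − 52 = 8 weeks | 60 − 48 = 12 weeks |

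Neither rule keeps an 8-week interval, which would fall at Week 56.

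**Does the general sentence in Section 6.1 reach groups not listed in its bullets?** It has to. Guselkumab and placebo PASI 90 nonresponders (Groups Ib and IIb) are not in the bullets either. Their doses run 20, 28, 36, 44, 52 (Group IIb also at Week 16), so the general sentence correctly gives them Week 52 on an 8-week cycle. It is the only Section 6.1 extension rule they have, and nothing in it separates them from the etanercept crossovers.

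**The cut-off in the first bullet of Section 6.1.** It says before Week 52, where footnote j and Section 8 say before Week 48. A participant who relapses and is retreated at Week 48 literally meets the first bullet (no Week 52 dose) and the second (a Week 52 dose). The second bullet, footnote j and Section 8 together make the intended Weeks 48, 52 and 60 clear, so this is a wording slip.

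**How many.** Planned etanercept arm: 15 + 10 = 25. As a share of the planned minimum of 100 exposed to guselkumab: 25/100 = 25%. Both are ceilings, because they assume that every etanercept participant elects guselkumab and enters the extension. The documents give no uptake figure. Assuming 50% to 90%: 0.5 × 25 = 12.5 and 0.9 × 25 = 22.5, so about 12 to 23.

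**The case against.** The strongest reply is that Section 6.1 omits the crossovers and does not contradict Section 8. It never names them, the Week 52 dose is inferred from a general sentence, and Section 8 states a specific exception that they plainly meet. The rest of the protocol points the same way: Group III dosing ends at Week 48 while the other Part 1 groups run through Week 52, and others dosed at Week 48 before entry resume at Week 60. On this view a site would have to read one sentence in isolation to go wrong, and the documents do not show that any did.

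Much of this stands. Week 60 is very probably the intent, and the cause is an omission in Section 6.1. The silence argument fails, though: the same general sentence is what doses Groups Ib and IIb, so it operates on unlisted groups. Section 6.1 is where the protocol sets out study interventions, and its extension text does not refer the reader to Section 8.

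Three further limits are fair:

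- Week 60 readings will mix 8 and 12 weeks since last dose even after correction, because Groups Ib and IIb and Part 2 are dosed at Week 52 while some retreated participants are dosed at Week 48.
- The safety-set point applies equally to retreated participants who skip Week 52, and no frequency is available for leaving between Weeks 52 and 60.
- Enrollment is closed (Protocol Appendix 2), and the documents do not say how many crossovers have yet to reach Week 52.

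**Conclusion.** The concern holds. As written, Section 6.1 puts the next crossover dose at Week 52 and Section 8 puts it at Week 60: 4 against 12 weeks after Week 48, or one additional injection. The footnotes to the Schedule of Activities do not settle it. Section 8 fits the rest of the protocol, so Section 6.1 is the text to correct.

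Reach is limited to at most 25 planned participants, or about 12 to 23 under the assumed 50% to 90% uptake. The affected outputs are descriptive, and the Week 16 co-primary and major secondary analyses are untouched. It should be corrected because it governs whether a child gets an additional dose and the correction is small. If every crossover is already past Week 52, the text change is mainly for the record, but reporting what was given still matters.

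**What to change.** 1. In the first extension bullet of Section 6.1, extend the exception to participants randomized to etanercept who receive guselkumab at Week 48: no Week 52 dose, next dose at Week 60, then every 8 weeks.
2. In the same bullet, change the cut-off from Week 52 to Week 48, to match footnote j and Section 8.
3. Add the crossovers to footnote j of Section 1.3.1, so that the schedule states the rule too.
4. For crossovers already past Week 52, report the schedule actually given.
5. Optionally, in SAP Section 5.5.2.3, show the Week 60 summaries by week of last dose (48 or 52). This would also display the mixture that remains after the correction. Splitting the retreatment summary by relapsed or not relapsed is a further option, but it concerns participants withdrawn from guselkumab, not the crossovers.

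The cost is one sentence and one cut-off in Section 6.1, plus a phrase in footnote j. The SAP item is one descriptive table.
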